### **9.2.8.7 Concomitant medication**

Definition of concomitant medication: any other medication, including other hormone replacement treatment, than Sogroya® (somapacitan) that is taken during the study, including at baseline (visit 1)

Details of all concomitant medication must be recorded at study entry (i.e. at baseline, visit 1) in the eCRF. Any changes in medication must be recorded at each visit (assessment visits, phone visits and end of study visit) in the eCRF.

The information collected for each concomitant medication should preferably include trade name or generic name, indication, start and stop date or continuation. For medications containing oestrogen also the route of administration must be recorded. If a concomitant medication is taken because of an adverse event this must be listed in the eCRF.

### **9.2.8.8 Dosage, titration, and adherence**

The Sogroya® (somapacitan) dosing information at study entry and any changes to the dosing during the study must be recorded in the eCRF. For patient naïve to Sogroya® (somapacitan)

Protocol  
 Study ID: NN8640-4515  
 UTN: U1111-1264-8642  
 EU PAS No: Pending

**CONFIDENTIAL**

Date:	15 February 2022	Novo Nordisk
Version:	3.0	
Status:	Final	
Page:	26 of 53	

treatment when entering the study, details of titration regimen of Sogroya®(somapacitan) should be recorded in the eCRF when available. Patients' adherence will be recorded in the eCRF at each visit by an average missed dose per 2 months ( $\leq 1$  dose,  $1 <$  and  $< 3$  doses or  $3$  doses  $\leq$ ) based on physician asking the patient.

### 9.2.8.9 Patient reported outcomes

Patient reported outcomes (PRO) questionnaires will be used to assess patient functioning and well-being, sick days and physician visits, impact on work and study productivity and the ability to do regular daily activities in patients on Sogroya® (somapacitan) treatment.

The PRO questionnaires should be completed by patients preferably at baseline visit, each subsequent visit and at the end of the study visit. PRO questionnaires should preferably be completed at a visit before any other study-related activities.

The questionnaires will be provided in local language and take approximately 10 minutes to complete.

After completion, the PROs must be reviewed by the physician on the same day for potential AEs, including any overall change in health and concomitant medication. When reviewing the PRO questionnaires for AEs the investigator should not influence nor question the patient on the content of the patient's response to PRO questions.

If clarification of entries in the PRO questionnaires is needed, the patient should be questioned, and a conclusion made in the patient's medical record. Only the subject can make changes in the PRO. Care should be taken not to bias the patient. Filled in questionnaires will be entered in the eCRF by physician/site staff.

### TRIM-AGHD

Treatment Related Impact Measure-Adult Growth Hormone Deficiency (TRIM-AGHD) is a disease specific questionnaire which measures the impact of GH treatment on the functioning and well-being of adults with growth hormone deficiency . The four concepts covered by the questionnaire are physical health, energy levels, cognitive ability and psychological health. TRIM-AGHD has 27 items and a total score as well as domain specific scores can be derived. TRIM-AGHD is scored so that a lower score indicates a better health state. Scale range: 0 (best) - 100 (worst)

### AGHD WSI

AGHD Work Study Impact (AGHD-WSI) is a disease specific questionnaire which measures the number of sick days and visits to a physician, the impact on work and study productivity and the ability to do regular daily activities of Sogroya® (somapacitan) treatment. The questionnaire has two parts: the patient will complete the first part at the first visit, and the second part at all subsequent visits. For the questions on impact of AGHD on productivity at work or school, and the ability to do regular daily activities, it is measured so that a lower score indicates a better health state. Scale range 0 (best) - 10 (worst).

Protocol  
 Study ID: NN8640-4515  
 UTN: U1111-1264-8642  
 EU PAS No: Pending

**CONFIDENTIAL**

Date: 15 February 2022 | **Novo Nordisk**  
 Version: 3.0  
 Status: Final  
 Page: 27 of 53

### 9.2.8.10 Clinical Response evaluation

At each visit the physician will evaluate the clinical response and record whether there is a satisfactory clinical response as Yes or No in the eCRF.

### 9.3 Variables

Data within safety (AEs), clinical parameters and PRO questionnaires will be collected. Data and results from assessments and laboratory analyses will be recorded if performed according to routine clinical practice at the participating sites.

Ongoing monitoring will ensure that all collected data will be transferred to the eCRF as relevant.

### 9.4 Data sources

It is the intention of this non-interventional PASS to observe long-term routine treatment of the individual patient. Data and results available in the patient's medical record and from assessments and laboratory analyses performed according to routine clinical practice at the participating sites will be recorded in the eCRF.

Data sources are patients medical record, eCRF, paper PROs, paper CRF form (Pregnancy and pregnancy outcome form) and local laboratory data. The systems used for this is validated according to internal Novo Nordisk procedures.

### 9.5 Study sample size

#### Sample size calculations

The following table shows the 95% confidence interval for an incidence between 0% and 5%, like e.g. the incidence of neoplasm:

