**Table 1 Sample size calculations**

Sample size		Observed incidence					
		0%	0.5%	1%	2%	3%	4%
100	<3	-	0 – 5.4	0.2 – 7.0	0.6 – 8.5	1.1 – 9.9	1.6 – 11.3
200	<1.5	0 – 2.8	0.1 – 3.6	0.5 – 5.0	1.1 – 6.4	1.7 – 7.7	2.4 – 9.0
400	<0.75	0.1 – 1.8	0.3 – 2.5	0.9 – 3.9	1.6 – 5.2	2.3 – 6.4	3.1 – 7.6
600	<0.50	0.1 – 1.5	0.4 – 2.5	1.0 – 3.5	1.8 – 4.7	2.6 – 5.9	3.4 – 7.1

Using the observed incidence for neoplasm of 2% in the NordiNet® IOS with somatropin as reference values, a sample size of about 400 patients would be required to rule out the doubling of incidence for neoplasm. In general, the table shows that the precision, i.e. the change for the upper limit of the confidence interval, is having a large decrease when changing from 200 to 400 patients,

Protocol  
 Study ID: NN8640-4515  
 UTN: U1111-1264-8642  
 EU PAS No: Pending

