**CONFIDENTIAL**

Date:	15 February 2022	Novo Nordisk
Version:	3.0	
Status:	Final	
Page:	28 of 53	

while the change from 400 to 600 patients is not having the same impact on the precision. Therefore, the study is planned for the sample size of 400 patients.

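### Table 1 (section 9.5) has one wrong upper limit (600 patients at 1%) and a 0% column of unlabelled one-sided limits among two-sided intervals; N = 400 is not affected

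*Protocol*

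**What the plan says.** Section 9.5 opens its sample size argument with "The following table shows the 95% confidence interval for an incidence between 0% and 5" (per cent). One confidence level is given for the whole of Table 1. Sidedness is not stated, and no separate rule is given for zero events.

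Two arguments then lead to the sample size:

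- **Ruling out a doubling.** The text begins "Using the observed incidence for neoplasm of 2% in the NordiNet" IOS registry and concludes that "a sample size of about 400 patients would be required to rule out the doubling of incidence for neoplasm". This uses the 2% column, where the upper limit for 400 patients is printed as 3.9, below the doubled value of 4%.
- **Diminishing precision.** The text judges precision by how far the upper confidence limit falls. It finds a large fall from 200 to 400 patients, "while the change from 400 to 600 patients is not having the same impact on the precision". It ends: "Therefore, the study is planned for the sample size of 400 patients".

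The entries at issue are the 0% column, printed <3, <1.5, <0.75 and <0.50 for 100, 200, 400 and 600 patients, and the cell for 600 patients at 1%, printed 0.4 to 2.5. The cell above it, 400 patients at 1%, is printed 0.3 to 2.5.

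**The concern.** Two parts of the table do not follow the method used in the rest of it.

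In the 1% column the upper limit is 2.5 for both 400 and 600 patients. An exact interval at the same observed proportion must narrow when the sample grows by half, and every other non-zero column does narrow. The error also favours the protocol's own argument, since it makes the step from 400 to 600 look worthless at 1%.

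The 0% column equals 3 divided by the sample size. That is a limit with 5% error in one tail, whereas the other columns put 2.5% in each tail. A reader who takes the table at its heading would read zero events in 400 patients as excluding incidences above 0.75% at the same confidence as the other cells. In a safety study whose primary endpoints include neoplasms and adverse drug reactions summarised by preferred term, that row may well be consulted.

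**Working it through.** **Inputs.** Sample sizes 100, 200, 400 and 600, and the printed limits, all from Table 1. The text read from the PDF shows six incidence labels over seven columns. The introductory sentence runs from 0% to 5%, and recomputation identifies the columns as 0, 0.5, 1, 2, 3, 4 and 5%. The missing label is treated as an effect of extraction.

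**Step 1: identify the method.** For x events in n patients the two-sided 95% Clopper-Pearson limits are:

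- lower = 2.5% quantile of Beta(x, n − x + 1)
- upper = 97.5% quantile of Beta(x + 1, n − x)

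| Cell | x/n | Computed (%) | Printed (%) |
|---|---|---|---|
| 100, 5% | 5/100 | 1.64–11.28 | 1.6–11.3 |
| 200, 2% | 4/200 | 0.55–5.04 | 0.5–5.0 |
| 400, 1% | 4/400 | 0.27–2.54 | 0.3–2.5 |
| 400, 2% | 8/400 | 0.87–3.90 | 0.9–3.9 |
| 600, 2% | 12/600 | 1.04–3.47 | 1.0–3.5 |

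Of the 23 printed intervals, 22 agree within rounding. The dash for 100 patients at 0.5% is correct, since half a patient cannot be observed.

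**Step 2: the exception, 600 patients at 1% (6/600), printed 0.4–2.5.**

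| 95% method | Interval (%) |
|---|---|
| Clopper-Pearson | 0.37–2.16 |
| Wilson | 0.46–2.16 |
| Wilson, continuity-corrected | 0.41–2.28 |
| Agresti-Coull | 0.40–2.22 |
| Jeffreys | 0.42–2.05 |
| Exact Poisson | 0.37–2.18 |
| Wald | 0.20–1.80 |

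None reaches 2.5. A neighbouring count does not explain it either: 7/600 gives 0.47–2.39 and 8/600 gives 0.58–2.61. The printed 2.5 equals the upper limit one row above.

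**Step 3: effect on the precision comparison (upper limits, %).**

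| Column | 200 | 400 | 600 | 200 to 400 | 400 to 600 |
|---|---|---|---|---|---|
| 1%, printed | 3.6 | 2.5 | 2.5 | 1.1 | 0 |
| 1%, computed | 3.57 | 2.54 | 2.16 | 1.03 | 0.38 |
| 2%, computed | 5.04 | 3.90 | 3.47 | 1.14 | 0.43 |

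The gain missing at 1% is 0.38/2.54, about 15% of the 400-patient limit.

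**Step 4: the 0% column.** With zero events the one-sided 95% limit is 1 − 0.05^(1/n), which is close to 3/n. The upper end of the two-sided 95% exact interval is 1 − 0.025^(1/n).

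| n | Printed | 3/n | One-sided 95% | Two-sided 95% |
|---|---|---|---|---|
| 100 | <3 | 3 | 2.95 | 3.62 |
| 200 | <1.5 | 1.5 | 1.49 | 1.83 |
| 400 | <0.75 | 0.75 | 0.746 | 0.92 |
| 600 | <0.50 | 0.50 | 0.498 | 0.61 |

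The printed column is 3/n. Against the two-sided limits it is lower by 17% (1 − 3/3.62) to 18% (1 − 0.75/0.92).

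In terms of error: if the true incidence is 0.75%, the chance of no event in 400 patients is 0.9925^400 = 0.049, against the 0.025 upper-tail error behind the other columns. A two-sided limit of 0.75% would need ln(0.025)/ln(0.9925), about 490 patients.

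**The case against.** The strongest reply is that nothing in the protocol turns on either item. The sample size rests on the 2% column, which is right. The precision sentence describes the table in general, and the other non-zero columns show the gain from 400 to 600 openly (1.8 to 1.5, 3.9 to 3.5, 5.2 to 4.7, 6.4 to 5.9, 7.6 to 7.1). With the cell corrected, the 1% column reads 3.6, 2.5, 2.2 and the sentence remains true. All of this stands, and it keeps the severity low.

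On the 0% column, the reply is that only an upper bound is informative with zero events, that the table signals this by printing a less-than sign instead of a range, and that 3/n is a correct one-sided 95% bound. This also stands: the column is not miscalculated. What remains is that one heading covers two error levels without saying so, and that the zero-event limits look tighter than they would on the basis of the other columns.

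The table header is visibly damaged in the extracted text, so a misread digit cannot be wholly excluded. The cell should be compared with the source before it is edited. The neighbouring cells in the same row and column all reproduce, which makes a shifted column unlikely.

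Two stronger readings are tempting. A reader might infer that N = 400 is undermined because Table 1 supports it; the correct 2% column rules that out. A reader might also infer that the reports will claim too much about events never seen. Section 9.7.2.1 plans counts, percentages and rates, and nowhere in the protocol is 0.75% used or an exclusion rule set for zero events.

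**Conclusion.** The point holds as a low-severity correction to Table 1. One cell is wrong: the upper limit for 600 patients at 1% is 2.2, not 2.5, which hides a gain of 0.4 points. One column follows a different, unlabelled convention: on the two-sided basis of the rest of the table, zero events in 400 patients excludes incidences above 0.92%, where 0.75% is printed.

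Neither affects the planned 400 patients. The 2% upper limits of 5.0, 3.9 and 3.5 are correct, and the step from 400 to 600 (0.4 points at 1%) stays smaller than the step from 200 to 400 (1.0 point).

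The conclusion assumes the column order given in the working and that the two-sided exact interval is the table's intended convention, as 22 of its 23 intervals indicate. If one-sided limits were meant for zero events, the 0% figures are correct and only the label is missing.

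**What to change.** In Table 1 of section 9.5:

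1. Correct the cell for 600 patients at 1% to 0.4 – 2.2.
2. Replace the 0% column with the two-sided 95% exact upper limits: <3.6, <1.8, <0.92 and <0.61. As second best, keep the printed values and label the column *one-sided 95%*.

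The cost is five table cells, or one cell and a label. Patients, data collection, endpoints, analyses and the sample size are unchanged. With the replacement, the stated zero-event precision at 400 patients becomes slightly less favourable (0.92% instead of 0.75%). No new reporting rule for the interim or final reports is needed.

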**Table 1 Sample size calculations**

Sample size		Observed incidence					
		0%	0.5%	1%	2%	3%	4%
100	<3	-	0 – 5.4	0.2 – 7.0	0.6 – 8.5	1.1 – 9.9	1.6 – 11.3
200	<1.5	0 – 2.8	0.1 – 3.6	0.5 – 5.0	1.1 – 6.4	1.7 – 7.7	2.4 – 9.0
400	<0.75	0.1 – 1.8	0.3 – 2.5	0.9 – 3.9	1.6 – 5.2	2.3 – 6.4	3.1 – 7.6
600	<0.50	0.1 – 1.5	0.4 – 2.5	1.0 – 3.5	1.8 – 4.7	2.6 – 5.9	3.4 – 7.1

Using the observed incidence for neoplasm of 2% in the NordiNet® IOS with somatropin as reference values, a sample size of about 400 patients would be required to rule out the doubling of incidence for neoplasm. In general, the table shows that the precision, i.e. the change for the upper limit of the confidence interval, is having a large decrease when changing from 200 to 400 patients,

Protocol  
 Study ID: NN8640-4515  
 UTN: U1111-1264-8642  
 EU PAS No: Pending

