**CONFIDENTIAL**

Date: 15 February 2022 **Novo Nordisk**  
 Version: 3.0  
 Status: Final  
 Page: 12 of 53

The duration of the study is planned with patient participation for 5 years or longer up to a total study duration of 10 years, if possible. The main purpose of the study is to observe patients for long-term safety.

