**Figure 1 Study Design**

**Note:** symbol (  ) Represents interim reporting

The study is planned to collect a broad variety of safety and other clinical parameters data generated during routine clinical care visits and other relevant clinical contacts (e.g. phone calls between patient and clinical site) in AGHD patients treated with commercially available Sogroya® (somapacitan). The duration of the study is planned with patient participation for 5 years or longer up to a total study duration of 10 years, if possible. The main purpose of the study is to observe patients for long-term safety. It is however well known that adult patients on GH therapy, often interrupt or discontinue treatment. Due to this expected dropout from treatment, and in the context of the duration of the study, patients switching from or discontinuing treatment with Sogroya® (somapacitan) will be offered continuation in the study in order to collect post treatment data.

The current study will compare data from a non-interventional registry study (NordiNet® IOS) which was monitoring the long-term use of once daily Norditropin® as a historical comparison group consisting of approximately 2300 AGHD patients enrolled in Europe between 2006 and 2016.

The sample size estimation for this study is based on the incidences for neoplasms reported in Nordinet® IOS. It is estimated that a sample size of 400 patients will be required to rule out the doubling of incidence for neoplasms in patients treated with Sogroya® (somapacitan).

Data on concomitant medication, medical history (adult/ childhood onset of GHD), laboratory parameters including but not limited to hepatic, renal, heart and diabetes status as well as data on neoplasms and medication errors will be collected as part of this study if available per routine clinical practice in order to evaluate safety. Other data which are already available in the medical records or being obtained as part of routine clinical practice, such as IGF- I /IGFBP-3 values, measures of body composition and bone health and PROs, will be collected to support the evaluation of clinical parameters.

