## 9.2 Setting

### 9.2.1 Study population

Patients for this study will be included globally from centres in countries where patients will be treated with Sogroya® within the planned recruitment timelines of the study.

Planned number of patients to be included globally: 400

Planned number of patients to complete the study: 400

Anticipated number of patients to be included in each country: depending on availability and commercial uptake of Sogroya® in relevant countries.

Planned time period for the study: 15 Dec 2022-15 Dec 2032

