### 9.7.2 Statistical methods

#### 9.7.2.1 Analysis of primary endpoints

The primary endpoints are the number of Adverse Drug Reactions (ADRs), incident neoplasms, and incident T2D from baseline (week 0) up to end of study (week 520).

Frequencies of ADRs during the study period will be summarised by MedDRA SOC and PT. This summary is displayed with number and proportion of patients with at least one event, number of event and event rate (events per 100 patient-years of exposure).

The primary objective of the study is to evaluate safety of once weekly dosing of Sogroya® (somapacitan) in AGHD patients over a study period up to 10 years, and analysis of ADRs will be one of the tools for achieving this. Adverse drug reactions will be analysed using descriptive statistics based on the ‘on treatment’ observation period (primary evaluation) and ‘in-study’ observation period (secondary evaluation) within the study period. The ADRs will be summarised by treatment, MedDRA (Medical Dictionary for Regulatory Activities) system organ class and MedDRA preferred term. The descriptive statistics will include the number and percentage of patients who experienced ADRs, the number of events and rate per 100 person years. ADRs will be listed by treatment and patient with information on severity, relationship to study product and demographics. ADRs with onset before first dosing will be reported in a separate listing.

In addition, incidence rates will be calculated for the endpoints Neoplasm and Diabetes Mellitus type 2.

Results will be reported separately for treatment-naïve and prevalent users of GH replacement therapy, and patients with a history of neoplasia and diabetes mellitus 2 will be addressed in stratified analyses.

For historical reference the primary evaluation, i.e. the on-treatment analysis, will be compared to the same results reported from the Nordinet® IOS database. It is not expected that there will be big differences in the baseline characteristics between the Nordinet® adult population and the population investigated in this study. If there are big differences between baseline characteristics, a matching procedure will be considered when making the comparison. In addition, a sensitivity analysis will be performed, restricting the primary evaluation to a European population only.

Protocol  
 Study ID: NN8640-4515  
 UTN: U1111-1264-8642  
 EU PAS No: Pending

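### Section 9.5's claim that 400 patients rule out a doubling of neoplasm incidence has no time base and allows for no loss, while the planned comparison is of on-treatment incidence rates

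*Protocol*

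**What the plan says.** Section 9.5 starts from a registry figure, "Using the observed incidence for neoplasm of 2% in the" NordiNet registry, and concludes that "a sample size of about 400 patients would be required to rule out the doubling of incidence for neoplasm". Table 1 supports this with 95% confidence intervals for a proportion of patients; the entry for 400 patients at an observed 2% is 0.9 to 3.9. Section 9.1 repeats the conclusion as the basis of the sample size. Neither section states the follow-up over which the 2% arose or the follow-up of the 400 patients to which it is applied.

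Elsewhere in the Protocol:

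- Section 4.5 plans "patient participation for 5 years or longer up to a total study duration of 10 years". The footnote to the endpoint tables in section 9.1.1 allows anything from 1 week to 10 years.
- Section 9.2.1: "Planned number of patients to be included globally: 400", then "Planned number of patients to complete the study: 400".
- Section 9.1 says that adults on growth hormone often interrupt or stop. "Due to this expected dropout from treatment", patients who stop or switch are offered continued participation. Section 9.9 separately names loss to follow-up as a risk.
- Section 9.7.1 ends the on-treatment period at discontinuation.
- Section 9.7.2.1: "In addition, incidence rates will be calculated for the endpoints Neoplasm and Diabetes Mellitus type 2". The on-treatment evaluation is the one compared with the registry.

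**The concern.** A cumulative proportion grows with observation time. Setting 2% in one cohort against a doubling in another is meaningful only if the two were followed for similar periods, and section 9.5 does not say whether they were. The planned analysis is on a different scale: events per unit of on-treatment time, which varies between patients and is shortened by discontinuation. The sizing therefore does not describe the precision of the estimate that will be reported. It also has no allowance for patients lost from the study.

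Neoplasm is a primary endpoint of a safety study required by the regulator, and ruling out a doubling is the only quantitative claim made for the design. If it is carried into the reports as written, readers will credit the study with a precision that the Protocol has not established.

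**Working it through.** **1. Reproduce the plan's figure.** Exact (Clopper-Pearson) 95% interval for 8/400 = 2%: 0.87 to 3.90%, matching the printed 0.9 to 3.9. Doubling 2% gives 4%; the Protocol implies this limit but does not write it. At an observed 2%, in steps of 50 patients, the upper limit is 4.30% (6/300), 4.08% (7/350) and 3.90% (8/400), so 400 is the first step below 4%. The arithmetic for that cell is right.

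**2. How thin is the margin?** With 400 patients the upper limit stays below 4% only at 8 or fewer cases (9/400 gives 4.23%). Loss to follow-up (assumed sizes):

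- 350 evaluable, 7 cases (2%): upper limit 4.08%.
- 320 evaluable, 6 cases (1.9%): upper limit 4.04%.

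Both miss 4%. Even with 400 patients and a true 2%, the chance of 8 or fewer cases is 59%; section 9.5 states no power.

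**3. Effect of the missing time base.** The registry follow-up is not in the Protocol, so it is assumed to be F = 5, 4 or 3 years. With a constant hazard, λ = −ln(0.98)/F = 4.04, 5.05 or 6.73 per 1000 patient-years.

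On-treatment time here: recruitment from December 2022 to December 2027 and last visit in December 2032 (section 6) give T between 5 and 10 years, 7.5 on average if entry is even. With a yearly discontinuation hazard h (assumed; the Protocol gives no figure), mean on-treatment time is the average of (1 − exp(−hT))/h over T from 5 to 10:

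- h = 0.10: 5.23 years, or 400 × 5.23 ≈ 2090 patient-years.
- h = 0.15: 4.45 years, or 400 × 4.45 ≈ 1780 patient-years.

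The expected proportion is p = 1 − exp(−HR × λ × mean years), and the chance of 8 or fewer cases is taken from Binomial(400, p). Using the mean on-treatment time for every patient is a simplification.

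| Registry follow-up (assumed) | h | Expected proportion, HR 1 | P(≤8), HR 1 | P(≤8), HR 2 |
|---|---|---|---|---|
| 5 y | 0.10 | 2.1% | 54% | 1.5% |
| 5 y | 0.15 | 1.8% | 71% | 5.5% |
| 4 y | 0.10 | 2.6% | 28% | 0.1% |
| 4 y | 0.15 | 2.2% | 47% | 0.8% |
| 3 y | 0.10 | 3.5% | 6% | <0.1% |
| 3 y | 0.15 | 3.0% | 16% | <0.1% |

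With no drug effect, the chance of meeting the sizing criterion runs from 6% to 71%. What moves it is the ratio of on-treatment time here to follow-up in the registry.

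**4. The same inputs on the rate scale.** Expected events without excess risk are λ × patient-years: 7.2 to 8.4 (F = 5), 9.0 to 10.6 (F = 4) or 12.0 to 14.1 (F = 3). Using an exact Poisson interval against a fixed reference rate, power to exclude a rate ratio of 2 is about 58% at 8 expected events and first reaches 80% at about 12.5. More patient-time relative to the registry now improves the chance of a correct conclusion, whereas on the proportion scale it worsens it.

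**The case against.** The strongest reply is that the analysis already uses incidence rates, which carry their own time base, and that nothing in the Protocol makes a decision at 4% or at 8 cases. The ENCePP checklist marks hypotheses as not applicable and says that no measure of association is specified; the registry comparison is for historical reference; and section 9.9 undertakes to discuss comparability in the report. Section 9.5 also justifies 400 by the diminishing gain in precision beyond that number. All of this stands. It confines the defect to the sizing claim and the zero-loss assumption; it does not make the claim correct.

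Four stronger readings are tempting, and the documents do not support them:

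- *The criterion measures follow-up length rather than drug effect.* A cumulative proportion reflects both; the fault is that they cannot be separated.
- *A doubled hazard could easily pass.* Against a 5-year registry follow-up, a pass probability of 59 to 94% needs a mean on-treatment time of 2.5 to 1.5 years, which means a discontinuation hazard of about 0.37 to 0.66 per year. Nothing in the Protocol supports that.
- *A drug without excess risk would pass only 0.2 to 16% of the time.* That applies the full 7.5 years to a comparison that ends at discontinuation.
- *Expected treatment dropout contradicts 400 completers.* Those patients are offered continued participation. Only the loss to follow-up in section 9.9 conflicts with 400 of 400; discontinuation matters because it shortens on-treatment time.

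**Conclusion.** The concern holds for the sizing claim. Section 9.5 reproduces as binomial arithmetic, but it has no follow-up behind either proportion, rests on a plan with no loss, and sizes a different quantity from the one that section 9.7.2.1 compares. The margin, 3.90% against an implied 4%, is lost at 7/350 or 6/320.

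Under one consistent set of assumptions (constant hazard, even recruitment, 10 to 15% yearly discontinuation, registry follow-up of 3 to 5 years), a drug with no excess risk meets the criterion 6 to 71% of the time and a doubled hazard at most about 6%. The likelier error is therefore failing to rule out a doubling for a drug that carries no excess risk. These figures illustrate the sizing statement and do not predict a study decision. They turn on a registry follow-up that the Protocol does not give, so no single corrected sample size can be computed.

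This should be corrected in the Protocol and not left to a statistical analysis plan, because sections 9.5 and 9.2.1 themselves state the 2%, the conclusion and the 400 completers. A reader might go further and infer that the final neoplasm analysis is invalid or that 400 patients are too few; neither follows.

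**What to change.** 1. Restate section 9.5 on the rate scale: NordiNet first-neoplasm events and person-years; expected on-treatment and in-study person-years from 400 patients under stated discontinuation and loss rates; and the resulting precision for the rate ratio.
2. Restate or withdraw the claim of ruling out a doubling, here and in section 9.1, to match that precision.
3. In section 9.2.1, replace 400 completing with the number expected under the stated study-loss rate, kept separate from treatment discontinuation.

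The cost is a recalculation and protocol wording. The matching that section 9.7.2.1 contemplates already presupposes access to the registry data. No enrolment change is proposed. The downside is that the stated precision may turn out less favourable than section 9.5 now suggests.
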